**19.2 Describe what data are reviewed, including safety data, untoward events, and efficacy data.**

Response: Standard assessments of side effects, detailed records of adverse events, and overall rates of smoking cessation.

1497  
1498

**19.3 Describe any safety endpoints.**

Response: Standard assessments of side effects, detailed records of adverse events.

1499  
1500

**19.4 Describe how the safety information will be collected (e.g., with case report forms, at study visits, by telephone calls with participants).**

1501  
1502

Response: With case report forms at study visits.

**19.5 Describe the frequency of safety data collection.**

1503  
1504

Response: At all 6 clinic visits, which occur at 1- to 2-week intervals in the first 2 months of treatment.

**19.6 Describe who will review the safety data.**

1505  
1506  
1507

Response: As detailed in App10-02, study staff will review side effect reports at each study visit; standard decision rules are used to trigger reporting to the PI/Study Physician within 24 hours (often within minutes).

1508

**19.7 Describe the frequency or periodicity of review of cumulative safety data.**

1509 Response: Annually.

1510 *19.8 Describe the statistical tests for analyzing the safety data to determine whether harm is occurring.*

1511 Response: N/A. The base rates of serious adverse events are too small to be detected by statistical tests in  
1512 the proposed sample size.

1513 *19.9 Describe any conditions that trigger an immediate suspension of the research.*

1514 Response: Given the nature of the trial, it is hard to foresee conditions that would lead to immediate  
1515 suspension of the research. However, we would seek IRB input to consider immediate suspension if there  
1516 were more than 2 SAEs (Codes 3 and 4 in App10-02) determined to be probably/definitely related to study  
1517 participation during a single calendar month.

1518

1519 **20.0 Withdrawal of Subjects**

1520  N/A: This study is not enrolling subjects. This section does not apply.

1521

1522 *20.1 Describe anticipated circumstances under which subjects may be withdrawn from the research*  
1523 *without their consent.*

1524 Response: As described in the informed consent document:

1525 Can I be removed from the research without my OK?

1526 The principal investigator of the study can remove you from the research study without your approval.  
1527 Possible reasons for removal include:

- 1528 • The Principal Investigators feel it is necessary for your health or safety. Such an action would not  
1529 require your consent, but you would be informed if such a decision was made and the reason for this  
1530 decision.
- 1531 • You have not followed program requirements.
- 1532 • The Sponsor, University, or Investigators have decided to stop the program.

1533 *20.2 Describe any procedures for orderly termination.*

1534 *NOTE: Examples may include return of study drug, exit interview with clinician. Include whether*  
1535 *additional follow up is recommended for safety reasons for physical or emotional health.*

1536 Response: PI or designee will attempt to inform participants (by phone; if unable to contact, then by postal  
1537 service) of the reason for withdrawal. No additional follow-up is necessary; however, in some situations it  
1538 may be reasonable to provide alternative referral information, as discussed in other sections of the protocol.

1539 *20.3 Describe procedures that will be followed when subjects withdraw from the research, including*  
1540 *retention of already collected data, and partial withdrawal from procedures with continued data*  
1541 *collection, as applicable.*

1542 Response: As described in App10-02: "For all side effects that require attention, the site physician,  
1543 qualified medical staff and PI will determine a course of action (i.e., continuation and monitoring, dose  
1544 reduction, subject withdrawal). All side effects that are considered a Serious Adverse Event (see below)  
1545 will be reported to PIs and IRBs ..., as well as to the FDA and NIH (see below for protocol for adverse  
1546 event reporting)... PIs and Study Physicians will determine if any serious adverse event requires additional  
1547 care. Such events may be referred to the out-patient department ... or to the emergency department ...  
1548 (...have access to 24-hour emergency services, including extensive in-patient and out-patient services for  
1549 psychiatric conditions)."

1550

1551 **UPDATE 2020-06-30 – OPTIONAL SALIVA SAMPLE FOR GENETIC ANALYSIS:** As also noted  
1552 in Procedures and explicitly stated in the consent addendum: "If you say yes now, but you change your

1553 mind later, it will not be held against you or affect your participation in EVarQuit. You can always call  
 1554 [contact]) or email us ([contact]) to say that you have changed your mind, and the  
 1555 DNA sample will be destroyed.” In such an event, the PI ([name]) will contact [name] at the  
 1556 University of Toronto to ensure the deidentified sample is destroyed.

1557

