1218 information access to themselves. (When appropriate, we will remind participants that refusal to complete  
 1219 assessments may lead the study investigators to withdraw the participant from the trial.)

1220 Many of the measures will be self-administered, so participants will directly enter their responses into a  
 1221 computer/tablet/smartphone without the interviewer seeing their responses. This increases privacy and  
 1222 reduces potential discomfort.

1223 Participants will meet individually with study investigators and staff in private offices; privacy is enhanced  
 1224 by the swipe card security system (limiting access) and the white noise system (reducing concerns about a  
 1225 conversation being overheard).

1226 **UPDATE 2020-05-29: COVID-19:**

1227 For remote visits during the COVID-19 pandemic, the use of telemedicine technology (Zoom; telephone  
 1228 calls), we will advise participants to attend the visit in a private setting. Zoom meetings will be password-  
 1229 protected, and a telephone (audio-only) option will be available.

1230 **UPDATE 2020-06-30 – OPTIONAL TROUBLESHOOTING SOFTWARE:** As noted above,  
 1231 participants will have the option to download the TeamViewer app to assist with EMA app troubleshooting.  
 1232 The purpose of this software is to allow research staff to navigate to the EMA app and its settings to  
 1233 address problems more quickly and remotely so participants are less likely to miss assessments which could  
 1234 negatively impact their study eligibility and payment. The TeamViewer software will not be used for any  
 1235 other purposes beyond addressing problems with the EMA app. Staff will not access private information on  
 1236 the participant phone, such as photos, email, or texts messages, nor will they access functions such as the  
 1237 phone's camera. Participants have the option to decline having this app installed on their device.  
 1238 Additionally, the TeamViewer app requires the participant to actively consent to a troubleshooting session  
 1239 by clicking a pop-up to allow access each time research staff requests a remote access session. The  
 1240 participant can also end the remote session at any time.

1241 16.2 *Indicate how the research team is permitted to access any sources of information about the subjects.*

1242 *NOTE: Examples of appropriate responses include: school permission for review of records,  

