We will use a two-tiered system to assess potential side effects and adverse events. At each clinic visit, participants will complete an established checklist of symptoms and an open-ended evaluation for potential adverse events. Study staff will be trained to follow the procedures in App10-02 to trigger timely reporting of side effects and potential AEs to the Study Physician. Participants will also be given information (verbally and in a reminder wallet card) regarding how to contact the study personnel and under what circumstances to proceed to the emergency department. At any time, participants will have the option to stop taking the study medication and can drop out of the study if they desire. In addition, if any adverse event requires treatment and follow-up, participants will be provided with appropriate referrals. The Study Physician will determine the course of action for the subject reporting a serious adverse event (e.g., discontinuing medication, dose adjustment). The PI or Study Physician/Clinical Research Nurse will clinically follow all subjects who are discontinued due to a serious adverse event until the event is resolved.

1485  
1486  
1487  
1488  
1489

In accordance with NIH and IRB guidelines, this study will employ the following mechanisms for adverse event reporting: 1) alert the site IRBs of any and all reports of serious adverse events; 2) inform all members of the study team of any and all reports of serious adverse events; and 3) notify NIH of any actions taken by IRBs with regard to data safety monitoring. Detailed procedures are formalized in App10-02.

1490  
1491  
1492  
1493

Although we considered establishing a formal DSMB, this does not appear to be warranted for the current single-site trial that employs varenicline for its approved indication, smoking cessation. However, we do plan to summarize and review rates of side effects, adverse events, and efficacy data – all blind to treatment condition – as part of each renewal application to the IRB.

1494  
1495  
1496

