 1582 caution driving or operating machinery until they are comfortable with how Chantix might affect them.  
 1583 Chantix should not be used with other quit-smoking products.

1584 Some people have had reported changes in behavior, including hostility, agitation, depressed mood,  
 1585 suicidal thoughts or actions while using Chantix to help them quit smoking, with these symptoms  
 1586 developing when they began taking Chantix, and on occasion after several weeks of treatment or even after  
 1587 stopping Chantix. Participants will be counseled on these potential risks and encourage to contact us if they  
 1588 and/or their family/friends notice agitation, hostility, depression, or changes in behavior, thinking, or mood  
 1589 that are not typical, or if they develop suicidal thoughts or actions, anxiety, panic, aggression, anger, mania,  
 1590 abnormal sensations, hallucinations, paranoia, or confusion.

1591 Varenicline also carries “warnings and precautions” regarding cardiovascular events, interactions with  
 1592 alcohol, seizures, and accidental injury. Varenicline may be associated with an increased risk of certain  
 1593 cardiac and vascular side effects, including chest pain, heart attack, and stroke. These risks are rare and are  
 1594 still being studied to determine how real they are. However, our study staff follows strict procedures to  
 1595 monitor for the presence of these side effects, including monitoring blood pressure at each in person visit  
 1596 and asking specific side effect questions related to cardiovascular events (e.g. chest pain, weakness on one  
 1597 side, etc) during each telephone session.

1598 Because varenicline safety for an unborn baby is unknown, participants who are pregnant or nursing a  
 1599 baby, or planning to become pregnant, will be excluded from participation. All women of childbearing  
 1600 potential must agree to use an adequate form of contraception throughout the study and will be asked to  
 1601 take a pregnancy test at study intake. Women who become pregnant during the study will be removed from  
 1602 varenicline therapy but may still participate in counseling and study follow-up.

1603 Threats to privacy/confidentiality. Since self-report and biological data will be collected and stored as part  
1604 of this study, it is possible that subject privacy or confidentiality can be threatened.

1605

1606 **UPDATE 2020-05-29 - COVID-19:**

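### Section 20.2 waives follow-up after investigators remove a participant, which conflicts with Section 19.1 and leaves abstinence outcomes unsecured for people in the ITT set

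*Combined protocol and SAP*

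**What the plan says.** **Who may be removed.** Section 20.1, citing the consent form, states "The principal investigator of the study can remove you from the research study without your approval". Its listed reasons include health or safety and "You have not followed program requirements". Section 16.1 adds that refusing "assessments may lead the study investigators to withdraw the participant from the trial". Section 20.3, excerpting an appendix (App10-02), names subject withdrawal as one response to a side effect, beside continued monitoring and dose reduction.

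**What follows removal.** Section 20.2 says the participant will be told the reason, and then "No additional follow-up is necessary; however, in some situations it" may make sense to give referral information.

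**What other sections say.** Under Section 19.1 the PI, study physician or research nurse will "clinically follow all subjects who are discontinued due to a serious adverse event until the event is resolved". Under Section 21.1, women who become pregnant come off "varenicline therapy but may still participate in counseling and study follow-up", but Section 21.4 takes them out of the study. Section 21.1 also warns of mood and behaviour changes "developing when they began taking Chantix, and on occasion after several weeks of treatment or even after" the drug is stopped.

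**Analysis set.** Section 10.1 counts a participant as ITT from the dispensing of medication at Clinic Visit 1. Sections 17.1 and 17.2 refer to methods that accommodate missing data. They give no rule for participants whom the investigators remove, and none that counts missing outcomes as smoking.

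**The concern.** There are two problems. First, staff who act on Section 20 and staff who act on Section 19.1 would treat a participant removed for a serious adverse event differently. The two pregnancy passages raise the same difficulty.

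Second, these removals happen after randomisation and by the investigators' choice. People removed for poor tolerability or poor adherence probably have a different chance of quitting from those who stay. If their abstinence is not collected, the ITT set exists in name but lacks outcomes for a selected group. Up to Week -1 only the extended arm takes active drug, so removals for tolerability could differ by arm in that period.

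**Working it through.** **1. The passages side by side**

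| Situation | One passage | Another passage | Compatible? |
|---|---|---|---|
| Removed because of a serious adverse event | 20.2: no further follow-up, no exception | 19.1: followed to resolution | No |
| Becomes pregnant | 21.1: off drug, may stay in study follow-up | 21.4: removed from the study | No |
| Removed for a non-serious side effect or for not following requirements | 20.2: no further follow-up | 19.1: silent | No conflict, but follow-up is waived |
| Symptoms that appear after stopping | 20.2: no further follow-up | 21.1: risk disclosure that sets no follow-up rule | Tension only |

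**2. Whether the outcome is secured.** The prompt for 20.3 asks about data already collected and about partial withdrawal with data collection continuing. The response covers side-effect handling and destruction of the DNA sample. So a person can be ITT (10.1), be removed (20.1, 16.1 or 20.3), need no follow-up (20.2), and have no stated route to an EOT or 6M abstinence result.

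The Aim 1 model is a logistic regression on group, gender and their interaction. If only the outcome is missing and no other variables enter the likelihood, a participant without an outcome contributes nothing. The analysis then reduces to complete cases.

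**3. Size.** The plan has no figure to reproduce. It gives overall attrition of 5% at the target quit date (TQD), 18% at EOT and 25% at 6M. It does not split these by arm or by cause. The following is therefore an illustration.

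Assumptions: no true effect, abstinence p = 0.45 in both arms, and removed fraction w = 0.08 in the extended arm (about 13 of 160) against 0.04 in the standard arm (about 6 of 160). Abstinence among the removed, a, is 0.05 or 0.15.

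- Outcomes lost: observed rate = (p − w·a)/(1 − w)
- Removed counted as smoking: observed rate = p − w·a

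| a | Handling | Extended | Standard | Difference | OR |
|---|---|---|---|---|---|
| 0.15 | Lost | 0.438/0.92 = 47.6% | 0.444/0.96 = 46.3% | +1.4 points | 1.06 |
| 0.05 | Lost | 0.446/0.92 = 48.5% | 0.448/0.96 = 46.7% | +1.8 points | 1.08 |
| 0.15 | Smoking | 43.8% | 44.4% | −0.6 points | 0.98 |
| 0.05 | Smoking | 44.6% | 44.8% | −0.2 points | 0.99 |

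With equal w and equal a in the two arms, the OR is 1.00 under either handling.

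The assumed average removal, (8% + 4%)/2 = 6%, fits inside the planned 18% loss at EOT. It is slightly above the 5% planned for all causes by TQD. It is therefore a high assumption if the removals fall only in the run-in and retention to TQD goes as planned.

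**4. A wider check on loss from all causes, not only removal.** Assume no true effect, 40% abstinence, and an average loss of 18% that is 5 or 10 points higher in the extended arm.

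- If all lost participants smoke, the complete-case OR is 1.13 or 1.27, and counting missing as smoking gives 1.00.
- If lost participants abstain like the rest, the complete-case OR is 1.00, and counting missing as smoking gives 0.91 or 0.83.

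The direction depends on the handling rule, and the plan states none.

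**The case against.** Several counter-arguments carry weight.

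- **Additional follow-up in 20.2 may mean beyond Section 19.** Its prompt asks about safety follow-up, and Section 21.2 points to Section 19 for monitoring. This is a possible reading. But 20.2 neither refers to Section 19 nor makes an exception, so the two texts still need reconciling. The conflict with 19.1 covers serious adverse events only.
- **Removal is optional.** The wording is that investigators can remove, or that refusal may lead to withdrawal. The documented attendance and EMA minimums apply before randomisation. Sections 19.1 and 21.2 recognise stopping medication as a step of its own. A reader might infer that anyone with a mood reaction or missed assessments must be removed. The documents do not say that. They permit removal without securing the outcome when it happens.
- **The excerpt in 20.3 is partial.** It comes from an appendix that is not in these documents, so its omissions are weak evidence. The prompt on continued data collection is nonetheless unanswered in the protocol itself.
- **Late symptoms in 21.1.** A reader might call this a contradiction of 20.2. It is a risk disclosure, accompanied by encouragement to contact staff, and it sets no follow-up rule.
- **Greater loss in the extended arm.** A reader might take this as established. The exposure difference is about three pre-quit weeks, both arms take active drug from Week -1, and no rates by arm are given. Nothing links removal for not following requirements to arm. Blinding of staff limits deliberate differences, though it does not stop tolerability from differing.

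**Conclusion.** The point holds as a conflict in the text and a gap in outcome collection. Section 20.2 conflicts with 19.1 for participants discontinued because of a serious adverse event, and 21.1 conflicts with 21.4 on pregnancy. The protocol does not ensure that EOT and 6M abstinence is collected for ITT participants whom the investigators remove. That collection stops is an inference from removal plus the silence of 20.3; no passage says so outright.

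Bias in the treatment comparison is possible but not shown. It needs removal, or the outcomes of those removed, to differ by arm, and its sign depends on an unstated missing-data rule. Under the assumed removal rates it is small (OR 0.98 to 1.08) beside the planned effects of OR 1.3 to 2.3. The documents do not support a claim that the plan favours the extended arm. The amendment should still be made, because the change is cheap and protects the ITT comparison.

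**What to change.** 1. Reconcile 20.2 with 19.1, and 21.1 with 21.4, so that each situation has one statement on follow-up after stopping medication or being removed. The clinical content is for the study physician to settle.
2. In 20.1 to 20.3, distinguish stopping study medication or study procedures from withdrawing consent for follow-up. State that participants removed by the investigators who have not withdrawn that consent stay in the ITT set. They are still contacted at the planned EOT and 6M time points for the abstinence report and the verification sample.

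The cost is a wording amendment, a matching consent sentence, and a few extra contacts at time points that already exist. Side-effect questions at EOT and 6M should not be assumed to be part of this. Section 19.5 places safety collection at the six clinic visits, so adding such questions could be a new procedure.

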## 1558 21.0 Risks to Subjects

1559 *21.1 List the reasonably foreseeable risks, discomforts, hazards, or inconveniences to the subjects related  
 1560 to their participation in the research. Consider physical, psychological, social, legal, and economic  
 1561 risks. Include a description of the probability, magnitude, duration, and reversibility of the risks.*

1562

*NOTE: Breach of confidentiality is always a risk for identifiable subject data.*

1563 Response: The potential risks to participants, and their likelihood and seriousness, are described below.  
 1564 Participants can choose, as an alternative, to not enroll in this study. Overall, there is minimal risk for  
 1565 serious adverse reactions as a consequence of enrolling in this study.

1566 Assessments. Subjects may experience emotional distress during assessments from discussing feelings and  
 1567 attitudes about smoking or from learning about the risks from smoking. These events happen very rarely  
 1568 and in almost all cases are short-lived and of low intensity, lasting for 1-2 weeks. Study personnel will be  
 1569 alerted to expect this from a small number of subjects and will be trained to make referrals for mental  
 1570 health services as needed. Personnel will be trained to query for adverse emotional reactions during  
 1571 assessments and will be trained to deal with such reactions and to provide additional referrals if needed. In  
 1572 addition, if assessments indicate psychiatric concerns, referrals to appropriate psychological services will  
 1573 be provided.

1574 Withdrawal symptoms following cessation. Most participants will experience some nicotine withdrawal  
 1575 upon quitting. Symptoms include craving, anxiety, irritability, problems concentrating, appetite change and  
 1576 weight gain, and insomnia. Because all subjects will use varenicline, withdrawal severity should be  
 1577 reduced. Moreover, withdrawal symptoms typically decrease markedly within 1-2 weeks. Study counseling  
 1578 will advise participants of these symptoms and discuss methods to cope with them.

1579 Varenicline. In clinical trials, the most common side effects of Chantix include: nausea, sleep problems  
 1580 (trouble sleeping, changes in dreaming), constipation, gas, and vomiting. Chantix may also contribute to  
 1581 difficult sleeping, vivid, unusual, or strange dreams. Participants will be informed of the need to use  
 1582 caution driving or operating machinery until they are comfortable with how Chantix might affect them.  
 1583 Chantix should not be used with other quit-smoking products.

1584 Some people have had reported changes in behavior, including hostility, agitation, depressed mood,  
 1585 suicidal thoughts or actions while using Chantix to help them quit smoking, with these symptoms  
 1586 developing when they began taking Chantix, and on occasion after several weeks of treatment or even after  
 1587 stopping Chantix. Participants will be counseled on these potential risks and encourage to contact us if they  
 1588 and/or their family/friends notice agitation, hostility, depression, or changes in behavior, thinking, or mood  
 1589 that are not typical, or if they develop suicidal thoughts or actions, anxiety, panic, aggression, anger, mania,  
 1590 abnormal sensations, hallucinations, paranoia, or confusion.

1591 Varenicline also carries “warnings and precautions” regarding cardiovascular events, interactions with  
 1592 alcohol, seizures, and accidental injury. Varenicline may be associated with an increased risk of certain  
 1593 cardiac and vascular side effects, including chest pain, heart attack, and stroke. These risks are rare and are  
 1594 still being studied to determine how real they are. However, our study staff follows strict procedures to  
 1595 monitor for the presence of these side effects, including monitoring blood pressure at each in person visit  
 1596 and asking specific side effect questions related to cardiovascular events (e.g. chest pain, weakness on one  
 1597 side, etc) during each telephone session.

1598 Because varenicline safety for an unborn baby is unknown, participants who are pregnant or nursing a  
 1599 baby, or planning to become pregnant, will be excluded from participation. All women of childbearing  
 1600 potential must agree to use an adequate form of contraception throughout the study and will be asked to  
 1601 take a pregnancy test at study intake. Women who become pregnant during the study will be removed from  
 1602 varenicline therapy but may still participate in counseling and study follow-up.

1603 Threats to privacy/confidentiality. Since self-report and biological data will be collected and stored as part  
1604 of this study, it is possible that subject privacy or confidentiality can be threatened.

1605

1606 **UPDATE 2020-05-29 - COVID-19:**

1607 In the context of the pandemic, any interaction with another person or objects they have touched carries  
1608 some risk of transmission of SARS-CoV-2, the virus that causes COVID-19.

1609 In the case of remote visits, it is possible that subject privacy or confidentiality can be threatened.

1610 *21.2 Describe procedures performed to lessen the probability or magnitude of risks, including procedures*  
1611 *being performed to monitor subjects for safety.*

1612 Response:

1613 To further minimize the likelihood and severity of the aforementioned risks of varenicline:

1614 1. We will employ select exclusionary criteria. For example, potential participants will be screened for  
1615 current suicidal behavior and severe mood disorder and for very high levels of alcohol consumption.

1616 2. We will administer the standard varenicline dose run-in and will not exceed the standard dose of 1 mg  
1617 B.I.D.

1618 3. We will discuss the potential risks of varenicline with prospective participants, including their likelihood.  
1619 We will monitor self-reported side effects and Adverse Events at each of the clinic visits during the  
1620 treatment period. Study Physician /PI will be alerted to side effects /Adverse Events, following our  
1621 standardized protocol (see App10-02). The Study MD/PI will review the information provided by the  
1622 research staff and if applicable, will contact the study participant directly to gather more information and  
1623 determine the appropriate course of action for the subject. Ultimately, the Study Physician will decide if the  
1624 AE is related to study medication and whether the subject should discontinue taking study medication.

1625

1626 To protect privacy and confidentiality, we have several safeguards against unauthorized access to study  
1627 data – please see the sections of Privacy and Confidentiality sections of this document for details. We have  
1628 not experienced the unauthorized use of study data.

1629 Procedures for monitoring subjects for safety are presented in detail in Section 19.

1630 **UPDATE 2020-05-29: COVID-19:**

1631 Please see Section 11.1, above, for our extensive procedures to mitigate risk of transmission of SARS-  
1632 CoV-2, the virus that causes COVID-19, as well as our monitoring for COVID-19 symptoms.

1633 *21.3 If applicable, indicate which procedures may have risks to the subjects that are currently*  
1634 *unforeseeable.*

1635 Response: There may be risks that we do not know about at this time. We will notify participants of any  
1636 new information that may affect their willingness to continue participation in this study.

1637 *21.4 If applicable, indicate which research procedures may have risks to an embryo or fetus should the*  
1638 *subject be or become pregnant.*

1639 Response: Because varenicline safety for an unborn baby is unknown, participants will be told that they  
1640 should not become pregnant while on this study. Women on the study should not nurse a baby. If the  
1641 woman is of childbearing potential, she must use an adequate form of contraception while study medication  
1642 is being taken and for at least one month after the end of the trial. If the woman is pregnant or breast  
1643 feeding, she may not participate in this study, and if she becomes pregnant during the study, she will be  
1644 removed from the study. Women will be asked to take a pregnancy test before starting the study.

1645 *21.5 If applicable, describe risks to others who are not subjects.*

1646 Response: We are not aware of any risks of this research to others who are not subjects.

1647

1648 **22.0 Potential Benefits to Subjects**1649 *22.1 Describe the potential benefits that individual subjects may experience by taking part in the*  
1650 *research. Include the probability, magnitude, and duration of the potential benefits. Indicate if*  
1651 *there is no direct benefit.*1652 *NOTE: Compensation **cannot** be stated as a benefit.*

1653 Response: As described in the consent form –

1654 “Will being in this study help me in any way?

1655 We cannot promise any benefits to you or others from your taking part in this research. However, possible  
1656 benefits include learning more about your smoking habit and quitting smoking. All participants receive free  
1657 smoking cessation counseling and the most effective smoking cessation medication currently available  
1658 (varenicline).1659 This clinical research study may show us how to make it easier for other smokers to quit smoking with  
1660 varenicline in the future.”1661 **23.0 Compensation for Research-Related Injury**1662  *N/A: The research procedures for this study do not present risk of research related injury (e.g.*  
1663 *survey studies, records review studies). This section does not apply.*1664 *23.1 If the research procedures carry a risk of research related injury, describe the available*  
1665 *compensation to subjects in the event that such injury should occur.*

1666 Response: As described in the consent form, under What else do I need to know?:

1667 It is important that you tell your study doctor if you feel that you have been injured because of taking part  
1668 in this study. You can tell the doctor in person or call. You will get medical treatment if you are injured as  
1669 a result of taking part in this study. Your study doctor will explain the treatment options to you and tell you  
1670 where you can get treatment. Generally, this care will be billed to you, your insurance or other third party.  
1671 The University at Buffalo has no program to pay for medical care for research-related injury.1672 *23.2 Provide a copy of contract language, if any, relevant to compensation for research related injury.*1673 *NOTE: If the contract is not yet approved at the time of this submission, submit the current version here.*  
1674 *If the contract is later approved with **different language regarding research related injury**, you must*  
1675 *modify your response here and submit an amendment to the IRB for review and approval.*

1676 Response: N/A – There is no contract other than the consent form.

1677 **24.0 Economic Burden to Subjects**1678 *24.1 Describe any costs that subjects may be responsible for because of participation in the research.*1679 *NOTE: Some examples include transportation or parking.*

1680 Response: Free parking will be made available, so that is not an issue.

1681 As described in the consent form: “Neither you nor your insurance provider will be charged for costs of  
1682 any of the procedures performed for the purpose of this research study (e.g., screening procedures,  
1683 experimental procedures, medication, counseling, monitoring/follow-up procedures described above).”1684  *N/A: This study is not enrolling subjects, or is limited to records review procedures only. This*  
1685 *section does not apply.*1686 **25.0 Compensation for Participation**1687 *25.1 Describe the amount and timing of any compensation to subjects, including monetary, course*  
1688 *credit, or gift card compensation.*

1689

Response:

1690

As detailed in the consent form, under What else do I need to know:

1691

